#### 11.4 Exclusion Criteria

1. Evidence or history of clinically significant hematological, renal, endocrine, pulmonary, gastrointestinal, cardiovascular, hepatic, psychiatric, neurologic,

or allergic disease (including documented drug allergies, but excluding untreated, asymptomatic, seasonal allergies at time of dosing).

2. Participants with a history of hysterectomy
3. Participants who are pregnant, possibly pregnant or lactating
4. History of febrile illness within five days prior to first dose.
5. Any condition possibly affecting drug absorption (eg, gastrectomy or other significant alterations of the gastrointestinal tract)
6. A positive urine drug screen.
7. An untreated-positive test for syphilis, gonorrhea, or Chlamydia at screening.
8. Any clinically relevant laboratory chemistry or hematology result Grade 2 or greater according to the DAIDS Laboratory Grading Tables
9. Treatment with an investigational drug within 4 months preceding the first dose of study product.
10. History of regular alcohol consumption exceeding 14 drinks (1 drink = 5 ounces (150 mL) of wine or 12 ounces (360 mL) of beer or 1.5 ounces (45 mL) of spirits) per week.
11. Participation in a clinical trial involving rectal biopsies within 6 months preceding the first dose of trial medication.
12. Blood donation of approximately 1 pint (500 mL) within 56 days prior to dosing.
13. Any condition which, in the opinion of the investigator, is likely to interfere with follow-up or ability to take the study medication appropriately.
14. Unwilling or unable to comply with the dietary and concomitant drug restrictions in regard to study drug administration as outlined in the study procedures and prohibited medications sections.
15. Women utilizing continuous hormonal contraception options such as Seasonique, injectables, implants, and hormonal IUDs

## 11.5 Co-enrollment Guidelines

Participants cannot have participated in a clinical trial in which they received treatment with an investigational drug within 4 months preceding the first dose of trial medication or have participated in a clinical trial involving rectal biopsies within 6 months preceding the first dose of trial medication.

Figure 3 Truvada® Identification

## 12. Study Product

### 12.1 Study Product Description

Truvada® (Figure 3) is an FDA-approved pill that contains two different HIV medicines combined in one pill: emtricitabine and tenofovir disoproxil fumarate. Both medicines belong to the group of HIV drugs called nucleoside reverse transcriptase inhibitors (NRTIs) made by Gilead, Inc.

### 12.2 Administration

The participant will take a single oral daily dose of Truvada for the five days before Sampling Visit #1 and Sampling Visit #2 as scheduled. Doses can be given in person, or through video conferencing programs, such as SKYPE. A study team member will witness all doses and record the times of administration. The drug name and dose will be confirmed with visual inspection during a time-out procedure prior to dose administration.

### 12.3 Supply and Accountability

The medications will be purchased and dispensed by the Investigational Drug Service at UNC Hospitals.

### 12.4 Dietary Restrictions and Prohibited Medications and Practices

1. Participants must comply with a low fiber diet for 3 days prior to all rectal biopsies.
2. Participants must consume only clear liquids 12 hours prior to all rectal biopsies, refraining from anything containing red or purple dyes.

## 12.5 Toxicity Management

Laboratory tests will be taken before study drug administration to look for baseline abnormalities and these will be compared to the laboratory tests to be taken at the follow-up visit after study drug exposure. Any side effects will be managed symptomatically on a case by case basis. Participants will be advised to contact study staff if any adverse effects occur at any time during the study period and to seek medical attention as they see appropriate. A follow up call will be made by the research coordinator to assess for adverse events the day following any visits where a biopsy was performed.

## 12.6 Adverse Effects Associated with Use for Treatment of HIV Infection

### ***Emtricitabine***

Single dose emtricitabine safety data has not been published. For multiple doses, greater than 10% of patients have shown the following adverse effects: headache, dizziness, tiredness, inability to sleep, unusual dreams, loose or watery stools, upset stomach (nausea) or vomiting, abdominal pain, rash, itching, skin darkening of the palms and/or soles, increased cough, runny nose. Less than 10 % of patients experienced abnormal liver function tests, increases in pancreatic enzyme, increased triglycerides, and increased creatinine phosphokinase.

### ***Tenofovir disoproxil fumarate***

A phase I single-dose study with tenofovir 300 mg showed it was generally well tolerated. The most frequently reported adverse events were headache (19%) and

dizziness (13%). Flatulence (7%), hot flush (3%), and an increase in alanine aminotransferase (3%) were also reported.

### 13. Study Procedures

Study specific procedures are presented in table format in the Schedule of Events. All patients will attend an outpatient screening visit, an enrollment visit, two outpatient biopsy visits, and a follow-up visit. Dosing visits will occur in person or through videoconferencing. All on-site visits will be conducted at the UNC NC TraCS Clinical Translational Research Center. During the outpatient biopsy visits tissue will be collected by insertion of an anoscope for the rectal biopsies and rectal cells. We currently have a list of approximately 10 women who have expressed interest in participating in this study after having participated in a previous pharmacokinetic study where biopsies of this nature were collected. As part of the screening and informed consent process, every participant will receive a detailed description of the procedures involved and the intensity of the protocol.

#### 13.1 Pre-screening

Persons interested in participating will be pre-screened by telephone interview using a standardized IRB-approved questionnaire to assess general eligibility prior to scheduling a screening visit. Participants may be provided a copy of the informed consent prior to the screening visit, if requested.

#### 13.2 Screening Visit

After providing written informed consent, potential participants may be screened for eligibility.

The screening visit will consist of the following activities:

1. Review study overview and obtain written informed consent

2. Review approved contraception options to be used during the entire study period
3. Assign Participant ID
4. Collect demographic information
5. Collect medical/menstrual history and review contraception history
6. Perform physical exam
7. Vitals (blood pressure, heart rate, respiratory rate, height, weight (Safety vitals obtained on arrival to research clinic by nursing staff may be used))
8. Obtain safety labs:
  - a. CBC with differential (includes hemoglobin, hematocrit, WBC and differential count, platelets)
  - b. Coagulation studies (PT/INR and aPTT)
  - c. Serum Chemistry Panel (Sodium, potassium, chloride, bicarbonate, blood urea nitrogen, creatinine, serum glucose, total protein, albumin, aspartate aminotransferase, alanine aminotransferase, alkaline phosphatase, total bilirubin)
9. Serum Pregnancy Test
10. Urine Drug Test (amphetamine, barbiturate, benzodiazepine, cannabinoid cocaine, methadone, opiates)
11. Virology tests (HIV antibody combo, HBsAg, Hep C Ab)
12. STI tests (syphilis, gonorrhea, chlamydia)

### 13.3 Enrollment Visit

Within 42 days of the screening visit, all participants will present on their scheduled date for their enrollment visit. A repeat urine pregnancy test will be performed. If participant still meets eligibility criteria, the first dose of study drug will be administered by study staff, and they will be provided with 4 more doses to take home.

### 13.4 Biopsy Visit 1 and 2

Patients will be admitted to the Center for Translational and Clinical Research (CTRC) at University of North Carolina Chapel Hill Hospital at approximately Days 2-5 and 12-15 of their menstrual cycle, after 5 days of dosing study product.

This visit will consist of the following activities:

1. Targeted physical examination, as indicated
2. Vitals (BP, HR, RR, weight)
3. Urine Pregnancy test
4. Blood draw
  - a. Blood to be collected in one 3 mL K2 EDTA (purple top tube) and stored on ice for no more than 1 hour prior to processing blood plasma by centrifuging at 1700rcf (converts to 2800rpm) for 10 minutes at 4°C. Blood plasma will be aliquoted into an appropriately labeled cryovial and temporarily stored at -20°C until transferred to permanent storage at -80°C in the CPAC laboratory.
  - b. Blood to be collected in one 8 mL Cell Preparation tube (CPT) with Sodium Citrate and stored upright at room temperature for no more than 4 hours before transferring to the CPAC laboratory and initiating processing procedures for PBMCs as according to CPAC SOP0345.
  - c. Blood to be collected into one 6mL Serum Separator Tube (SST) and processed to serum by allowing to coagulate for 30 minutes at room temperature then centrifuging at 1700rcf (converts to 2800rpm) for 10 minutes at 4° C. Serum will be aliquoted into an appropriately labeled cryovial and temporarily stored at -20°C until transferred to permanent storage at -80°C in the CPAC laboratory.
5. Tissue samples will be obtained:
  - a. Digital exam will be performed prior to insertion of the anoscope. KY-jelly lubricant will be used for digital exam and anoscope insertion, but no anesthetic will be applied. Rectal cells will first be

collected with a cytobrush, placed immediately into a Falcon tube, and transported fresh back to the CPAC lab on ice. 10 biopsies will be collected from the rectal mucosa using 2.4mm radial jaw, single use, biopsy forceps by a board-certified gastroenterologist. Tissue will be transferred to two appropriately labeled, cryovials with 5 pieces of tissue in each cryovial. The samples will be transported fresh back to the CPAC lab on ice.

6. Adverse event assessment using a standard adverse events questionnaire will be conducted after the last sample is collected, prior to discharge to home.
7. Discharge to home

The patient will be offered a meal prior to discharge.

During Visit 1, the participant will be given a pill bottle containing the 5 doses of study product that they will take for the five days prior to Biopsy Visit 2, and dosing appointments will be scheduled.

The day following biopsies, each subject will be contacted in person/phone by a study team member to assess for adverse events. Additional study visits will be scheduled for any subject experiencing an adverse event.

### 13.5 Follow-up Visit

The follow up visit will consist of the following activities:

1. Targeted physical examination, as indicated
2. Vitals (BP, HR, RR, Temp and weight)
3. Safety labs:
  - a. CBC
  - b. Serum Chemistry Panel (Sodium, potassium, chloride, bicarbonate, blood urea nitrogen, creatinine, glucose, total protein, albumin, aspartate aminotransferase, alanine aminotransferase, alkaline phosphatase, total bilirubin)

- c. HIV test
- 4. Urine Pregnancy test

### 13.6 Behavioral Assessment

Adherence to behavior guidelines, approved contraception and medications taken will be assessed prior to the biopsies by a series of questions to be asked prior to proceeding. Women who do not have sex that could result in pregnancy, will only be tested at screening for pregnancy.

### 13.7 Clinical Evaluations and Procedures

The extent of examination for the brief physical exam will be determined by clinical judgment based on the interim medical history.

## 14. Assessment of Safety

### 14.1 Safety Monitoring

Adverse events will be monitored throughout the study. Adverse events will be assessed formally before discharge to home at the inpatient visit, after each outpatient visit and at the follow-up visit during which participants will answer standardized questions regarding to prompt reporting of adverse events associated with the study medication and procedures. The research coordinator will contact participants the day following all biopsy procedures.

### 14.2 Clinical Data and Safety Review

A multi-tiered safety review process will be followed for the duration of this study. The study site investigators are the first layer of this tiered system and are responsible

for the initial evaluation and reporting of safety information at the participant level, and for alerting the Protocol Safety Review Team (PSRT) if unexpected concerns arise. The PSRT will consist of the following study site investigators: [name] (Study Physician), [name], PA-C (Study Physician Assistant), [name] (Principal Investigator).

During the trial, the PSRT will review safety reports (all AEs included, independent of determination of relatedness to study products). In addition to these routine safety data reviews, the PSRT will convene on an ad hoc basis to make decisions regarding the handling of any significant safety concerns. If necessary, experts external to the protocol team, representing expertise in the fields of microbicides, biostatistics, and medical ethics may be invited to join the PSRT safety review.

#### 14.3 Adverse Events Definition and Reporting Requirements

An adverse event (AE) is defined as any untoward medical occurrence in a clinical research participant administered an investigational product and which does not necessarily have a causal relationship with the investigational product. As such, an AE can be an unfavorable or unintended sign (including an abnormal laboratory finding, for example), symptom or disease temporally associated with the use of an investigational product, whether or not considered related to the product. This definition is applied to all the study groups and is applied to all groups beginning from the time of consent. The term “investigational product” for this study refers to all study products. Study participants will be instructed to contact the study site staff to report any AEs they may experience at any time between consent and follow-up. In the case of a life-threatening event, they will be instructed to seek immediate emergency care. Where feasible and medically appropriate, participants will be encouraged to seek evaluation where the study clinician is based, and to request that the clinician be contacted upon their arrival. Study staff will obtain written permission from the participant to obtain and use records from non-study medical providers to complete any missing data element on a CRF related to an adverse event. All participants reporting an untoward medical occurrence will be followed clinically,

until the occurrence resolves (returns to baseline) or stabilizes.

The study physician will determine AE resolution or stabilization in their best clinical judgment. Study site staff will document in source documents all AEs reported by or observed in enrolled study participants regardless of severity and presumed relationship to study product. Study staff will record all AEs on case report forms.

#### 14.4 Serious Adverse Events

Serious adverse events (SAEs) will be defined by the Manual for Expedited Reporting of Adverse Events to DAIDS (Version 2.0, dated January 2010) as AEs occurring at any dose that:

1. Results in death
2. Is life-threatening
3. Results in persistent or significant disability/incapacity
4. Is a congenital anomaly/birth defect
5. Requires inpatient hospitalization or prolongation of existing hospitalization
6. The following are examples of hospitalization that will not be considered to be AEs:
  - a. Protocol-specified admission (e.g. for procedure required by study protocol)
  - b. Admission for treatment of target disease of the study, or for pre-existing condition (unless it is a worsening or increase in frequency of hospital admissions as judged by the clinical investigator)
  - c. Diagnostic admission (e.g. for a work-up of an existing condition such as persistent pretreatment lab abnormality)
  - d. Administrative admission (e.g. for annual physical)
  - e. Social admission (e.g. placement for lack of place to sleep)
  - f. Elective admission (e.g. for elective surgery)

Important medical events that may not result in death, be life-threatening, or require

hospitalization may be considered a serious adverse drug experience when, based upon appropriate medical judgment, they may jeopardize the patient or subject and may require medical or surgical intervention to prevent one of the outcomes listed above.

Study staff will report information on all AEs and SAEs to the IRB in accordance with all applicable regulations and requirements.

#### 14.5 Adverse Event Relationships

The relationship of all AEs to study product will be assessed per the Manual for Expedited Reporting of Adverse Events to DAIDS (Version 2.0, dated January 2010). Per the Manual for Expedited Reporting of Adverse Events to DAIDS (Version 2.0, dated January 2010), the relationship categories that will be used for this study are:

1. *Related*: AE and administration of study product are related in time, and a direct association can be demonstrated
2. *Possibly related*: There is a reasonable possibility that the adverse event, incident, experience or outcome may have been caused by the procedures involved in the research.
3. *Not related*: There is not a reasonable possibility that the AE is related to the study agent(s)

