### 15. Clinical Management

In general, the site investigator has the discretion to discontinue study product use/participation at any time if they feel that continued product use would be harmful to the participant or interfere with treatment deemed clinically necessary. Unless otherwise specified below, the investigator should immediately consult the PSRT for further guidance regarding permanent discontinuation.

The site investigator or designee will document all discontinuations on applicable case report forms.

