### 15.2 Discontinuation of Study Product in the Presence of Toxicity

Stopping rules have been created to protect the health and safety of study participants. If a single subject experiences a Serious Adverse Event, enrollment will be held while the protocol undergoes review. If 2 or more participants experience Grade 3 or Grade 4 adverse events, enrollment will be held while the protocol undergoes review.

Any Grade 3 or 4 or serious adverse event related to a study intervention (blood draw, biopsy) or the study drug will result in subject discontinuation. Participants who are withdrawn for safety reasons will complete a follow-up visit within 14 days the last sample collection visit.

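### Section 14.5 rates adverse events against the study product but defines *Possibly related* by research procedures, so the causality code is ambiguous for procedure injuries and possible drug reactions

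*Combined protocol and SAP*

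**What the plan says.** Section 14.5 (Adverse Event Relationships) opens with its scope: "The relationship of all AEs to study product will be assessed". It cites the DAIDS expedited reporting manual and then prints the scale, introduced by "the relationship categories that will be used for this study are". The three definitions are:

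- *Related*: "AE and administration of study product are related in time, and a direct association can be demonstrated".
- *Possibly related*, by contrast: "There is a reasonable possibility that the adverse event, incident, experience or outcome may have been caused by the procedures involved in the research".
- *Not related*: "There is not a reasonable possibility that the AE is related to the study agent(s" (the closing bracket is cut from the quote).

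No other relationship scale appears in the document. Section 15.2 attaches a consequence to relatedness and names two kinds of cause. Participant discontinuation follows from "Any Grade 3 or 4 or serious adverse event related to a study intervention (blood draw, biopsy) or the study drug".

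**The concern.** The first and third categories ask whether the drug caused the event. The second asks whether the research procedures did. A three-level scale should move along one question, from demonstrated through possible to not reasonably possible. This one changes the question in the middle.

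Elsewhere the protocol keeps the two causes apart. Section 14.1 asks about events linked to the medication and to the procedures, section 15.2 separates blood draw and biopsy from the study drug, and section 19.4 lists blood-draw, anoscopy/biopsy and drug risks under separate items. The word *procedures* in 14.5 therefore cannot safely be taken as a synonym for the product.

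At stake is whether a causality code on the case report form can be interpreted later. By each sampling visit a participant has had five days of drug and then undergoes blood draw, cytobrush and rectal biopsies, so both kinds of cause are present in every woman.

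**Working it through.** No figure in the plan bears on this point, so the check is logical. It takes the three definitions as printed in 14.5 and applies them to the kinds of event this design can produce. Three conditions decide the code: whether a direct drug association is demonstrated, whether a drug cause is reasonably possible, and whether a procedure cause is reasonably possible.

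The text allows three readings of *Possibly related*:

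- **A**: literal, with dosing not a procedure. This matches the usage in 14.1 and 15.2.
- **B**: literal, with dosing counted as a procedure.
- **C**: *procedures* taken to mean the study product, to fit the opening sentence of 14.5.

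| Event | Reading A | Reading B | Reading C |
|---|---|---|---|
| Drug cause possible but not demonstrated; no procedure cause | no category | Possibly related | Possibly related |
| Procedure cause (e.g. biopsy bleed); no reasonable drug cause | Possibly related and Not related | Possibly related and Not related | Not related |
| Drug and procedure both possible; neither demonstrated | Possibly related | Possibly related | Possibly related |
| Neither cause possible | Not related | Not related | Not related |

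Step by step for the two rows that go wrong:

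1. **Possible drug reaction.** *Related* fails because no direct association is demonstrated. *Not related* fails because a drug cause is reasonably possible. Under A, *Possibly related* also fails, because no procedure is suspected. Nothing is left. B and C close this gap.
2. **Procedure injury.** *Possibly related* is met under A and B because a procedure is suspected. *Not related* is also met because the agent is not. The double code therefore does not depend on whether dosing counts as a procedure. C removes it, but at a price: the biopsy bleed takes the same code as an event with no link to the study.

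A demonstrated drug reaction meets *Related* under every reading. It can also meet *Possibly related*: under A if a procedure cause is possible too, and under B in any case. Taking the stronger code settles that overlap. The same device does not settle the procedure injury, because coding it *Possibly related* on a scale meant for product asserts a drug link that the assessor has ruled out.

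Set against 15.2, reading C leaves a visible mismatch. A participant could be discontinued for a Grade 3 event related to biopsy while the only relationship scale in the protocol records that event as *Not related*.

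**The case against.** The best defence is that the opening sentence of 14.5 governs the list. The exercise concerns study product, so *Possibly related* should be read that way, and then every event gets exactly one code. This stands as far as it goes, and reading C is arguably the natural one. But the text does not say so, the printed words point elsewhere, and even on this reading the procedure causes used by 15.2 have no place on the scale.

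The second defence is that nothing stated in the protocol turns on the code. This largely stands:

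- The Protocol Safety Review Team (PSRT) sees all AEs whatever their relatedness (14.2).
- All AEs are documented and entered on case report forms (14.3), and information on them goes to the IRB (14.4).
- The enrollment holds in 15.2 count serious and Grade 3 or 4 events without mentioning relatedness.
- Discontinuation under 15.2 follows from either cause, so confusing the two does not change it.
- Under section 15, "the site investigator has the discretion to discontinue study product use/participation at any time". Unless a later subsection says otherwise, "the investigator should immediately consult the PSRT for further guidance regarding permanent discontinuation".

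A reader might infer that the discontinuation rule is disabled. The documents do not support that. Section 15.2 names drug and procedure itself, does not cite the 14.5 codes, and can be applied on clinical judgement.

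A reader might also point to a symptom that either drug or procedure could cause. That does not demonstrate the defect, because such an event is *Possibly related* under all three readings. It argues only for a separate procedure rating. Nor do the documents allow an estimate of how many events would be affected: the table lists logical kinds of event, and any tally of its rows would reflect how the kinds were chosen.

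**Conclusion.** The definition of *Possibly related* is wrong as written and should be corrected. The point is **minor**. Read literally, a procedure injury fits two opposing categories, and a possible drug reaction fits none unless dosing is a procedure. Read in scope, the codes are unique but procedure causality is not recorded.

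The harm is to the clarity of the causality record only. PSRT review, AE recording and the enrollment holds do not depend on the code. The PK endpoints in 10.5 and 10.6, the correlation analysis in 16.1 and the sample size of 10 women are untouched.

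The conclusion assumes that staff apply the categories as printed. The cited manual and the case report forms are not in the documents. Either could contain wording or a procedure field that reduces the problem, but 14.5 presents its own list as the one to be used.

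**What to change.** In 14.5, define *Possibly related* as a reasonable possibility that the study product caused the AE, without a demonstrated direct association. Then rate each AE separately for relationship to study procedures (blood draw, cytobrush, biopsy) on the same three categories, and record both ratings. A biopsy bleed would then be *Not related* to product with its own rating for procedure, and a possible drug reaction would be *Possibly related* to product. The record would then cover both kinds of cause that 15.2 uses.

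The cost is a wording change in 14.5, slightly more AE coding and, if the form does not already have it, one case report form field. No visit, test or participant is added.
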